### 19.4. LABORATORY EVALUATIONS

Results from the central laboratory will be included in the reporting of this study for Hematology, Blood Chemistry, Lipids, Coagulation, HbA1c, hsCRP and Urinalysis. A list of laboratory assessments to be included in the outputs is included in Protocol, [Section 10.1.6.1](#).

Presentations will use SI Units and conventional units.

Quantitative laboratory measurements reported as “< X”, i.e. below the lower limit of quantification (BLQ), or “> X”, i.e. above the upper limit of quantification (ULQ), will be converted to X for the purpose of quantitative summaries, but will be presented as recorded, i.e. as “< X” or “> X” in the listings.

The formula to calculate eGFR is:  $eGFR = 186 \times (\text{Creatinine} / 88.4)^{-1.154} \times (\text{Age})^{-0.203} \times (0.742 \text{ if female}) \times (1.210 \text{ if black})$ , where creatinine is in mmol/L.

Summaries for all lab results, including unscheduled visit values, will be included for below analyses:

- Observed and change/percent change from baseline by visit (for quantitative measurements).

[REDACTED]

Version Number: 1.7  
 Version Date: 21Mar2018

[REDACTED]

- Observed and change/percent change from baseline for HbA1c and glucose by history of diabetes and visit.
- Shift from baseline by visit according to normal ranges.
- Shift from baseline according to normal ranges for HbA1c and glucose by history of diabetes and visit.
- eGFR and values of CK will be summarized by treatment group and by baseline eGFR categories (low, normal, high).
- Potential Hy’s law cases (>3 × ULN for ALT and/or AST with concurrent Total Bilirubin >2 × ULN) will be tabulated listed.
- Laboratory abnormalities in parameters of interest

ALT or AST (> 3x ULN , >5xULN)

TB (>2x ULN)

CK (> 5x ULN) and (>10x ULN)

Fasting Blood Glucose (≤50 mg/dL, ≥126 mg/dL) by history of diabetes

HbA1c (≥6.5%) by history of diabetes

Creatinine (change from baseline for >1 mg/dL )

eGFR (< 15 mL/min/1.73m^2, 15 –< 30 mL/min/1.73m^2)

Hgb (decrease from baseline for ≥2 g/dL)

Hgb (<8 g/dL)

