6.2.2. Exclusion Criteria

1. Total fasting (minimum of 10 hours) TG ≥ 500 mg/dL (5.6 mmol/L at Week -5 (Visit S1)).

Note: A single repeat, fasting (minimum of 10 hours) of TG may be completed prior to initiation of the single-blind Run-in period. For those patients who have a repeat TG, the repeat value will be used to determine eligibility.

2. Renal dysfunction or a glomerulonephropathy, including estimated glomerular filtration rate (eGFR; using central laboratory determined Modification of Diet in Renal Disease [MDRD] formula) <30 mL/min/1.73 m² at Week -5 (Visit S1).

Note: A single repeat of eGFR may be completed between Visits S1 and S2. For those patients who have a repeat eGFR, the repeat value will be used to determine eligibility.

3. Body mass index (BMI) ≥ 50 kg/m²
4. Recent (within 3 months prior to the screening visit [Week -5 (Visit S1)] or between screening and randomization visits) MI, unstable angina leading to hospitalization, uncontrolled, symptomatic cardiac arrhythmia (or medication for an arrhythmia that was started or dose changed within 3 months of screening), coronary artery bypass graft (CABG), percutaneous coronary intervention (PCI), carotid surgery or stenting, cerebrovascular accident, transient ischemic attack (TIA), endovascular procedure or surgical intervention for peripheral vascular disease or plans to undergo a major surgical or interventional procedure (eg, PCI, CABG, carotid or peripheral revascularization). Patients with implantable pacemakers or automatic implantable cardioverter defibrillators may be considered if deemed by the Investigator to be stable for the previous 3 months.
5. Uncontrolled hypertension, defined as sitting systolic blood pressure (SBP) ≥ 160 mmHg and/or diastolic blood pressure (DBP) ≥ 100 mmHg measured according to local standards.

Note: At the discretion of the investigator, the time between Visits S1 and S2 can be extended by 4 weeks for adjustments in blood pressure (BP) medications and/or additional assessment of BP, with the repeat assessment value used to determine eligibility. Alternatively, patients can be rescreened if BP status has changed.

6. Hemoglobin A_{1C} (HbA_{1C}) $\geq 10\%$ at Week -5 (Visit S1).
7. Uncontrolled hypothyroidism, including thyroid-stimulating hormone (TSH) $>1.5 \times$ the upper limit of normal (ULN) at Week -5 (Visit S1). Patients stabilized on thyroid replacement therapy for at least 6 weeks prior to randomization are allowed.

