11.7. Safety Analysis

The summarization of AEs will include TEAEs, defined as any unfavorable and unintended sign, symptom, or disease temporally associated with the use of the investigational product, whether or not related to the product. TEAEs and SAEs will be summarized by SOC, severity, and relationship to study drug for each treatment group. These AE summaries will include cumulative incidence (percent of patients experiencing the AE) and patient-year adjusted incidence rates. If appropriate, absolute and relative risk differences will be calculated using both cumulative incidence and incidence rates. Deaths, withdrawal from study treatment due to AEs, and withdrawal from the study due to AEs will each be summarized by treatment group.

Clinical safety laboratories, including hematology, blood chemistry, coagulation, HbA_{1C}, glucose, and urinalysis; PE findings; vital signs; ECG readings; and weight will be summarized by the value and by change from baseline in the value (where appropriate) at each post baseline time point.

Hepatic Safety

For liver-associated enzymes and TB, the number and percent of patients with abnormal values for ALT, AST, and TB will be summarized. Hy's law criteria ($\geq 3 \times$ ULN for either ALT or AST, with accompanying TB $> 2 \times$ ULN (conjugated [direct] if Gilbert's Disease) in the absence

of other known causes) will also be applied to the data; any potential Hy's law cases will be listed separately.

Musculoskeletal Safety

AEs of muscle-related symptoms will be summarized by treatment group. In addition, the number and percent of patients with abnormal CK values will be summarized.

Diabetes/Glycemia

Cases of new onset of diabetes will be recorded as AEs and will be summarized using the appropriate SOC. These events will be summarized by severity and relationship to study drug for each treatment group.

Renal Safety

Baseline eGFR and values of CK will be summarized by treatment group and by baseline eGFR categories. Shift tables of eGFR category from baseline over the study, will be provided by treatment group. Finally, muscle-related AEs will be summarized by treatment group and by baseline eGFR category.

Neurocognitive Events

Neurocognitive events will be identified and evaluated by routine safety monitoring of PE findings and AEs. Summarization of neurocognitive events will occur using prespecified MedDRA terms and will be performed by treatment group.

Clinical endpoints

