Muscular disorders	Muscle spasms
Muscular disorders	Myalgia
Muscular disorders	Myoglobin blood increased
Muscular disorders	Myoglobin blood present
Muscular disorders	Myoglobin urine present
Muscular disorders	Myoglobinaemia
Muscular disorders	Myoglinuria
Muscular disorders	Myopathy
Muscular disorders	Myopathy toxic
Muscular disorders	Necrotizing myositis
Muscular disorders	Pain in extremity
Muscular disorders	Rhabdomyolysis
Neurocognitive/Neurologic disorders	Amnesia
Neurocognitive/Neurologic disorders	Cognitive disorder
Neurocognitive/Neurologic disorders	Confusional state
Neurocognitive/Neurologic disorders	Disorientation
Neurocognitive/Neurologic disorders	Memory impairment
Neurocognitive/Neurologic disorders	Mental status changes
Renal disorders	Acute kidney injury
Renal disorders	Acute prerenal failure
Renal disorders	Blood creatinine abnormal

[Redacted]

Version Number: 1.7  
 Version Date: 21Mar2018

[Redacted]

Adverse Event Terms per Protocol	Associated MedDRA Preferred Terms
Renal disorders	Blood creatinine increased
Renal disorders	Blood urea abnormal
Renal disorders	Blood urea increased
Renal disorders	Blood urea nitrogen/Creatinine ratio increased
Renal disorders	Creatinine renal clearance abnormal
Renal disorders	Creatinine renal clearance decreased
Renal disorders	Glomerular filtration rate abnormal
Renal disorders	Glomerular filtration rate decreased
Renal disorders	Gout
Renal disorders	Oliguria
Renal disorders	Prerenal failure
Renal disorders	Renal failure
Renal disorders	Renal function test abnormal
Renal disorders	Renal impairment

[Redacted]

Version Number: 1.7  
 Version Date: 21Mar2018

[Redacted]

Addendum to Statistical Analysis Plan

---

**Title:** A RANDOMIZED, DOUBLE-BLIND, PARALLEL GROUP, MULTICENTER STUDY TO EVALUATE THE EFFICACY AND SAFETY OF BEMPEDOIC ACID (ETC-1002) 180 MG COMPARED TO PLACEBO ADDED TO BACKGROUND LIPID-MODIFYING THERAPY IN PATIENTS WITH ELEVATED LDL-C WHO ARE STATIN INTOLERANT

**Protocol:** ETC-1002-046

**Clinical Phase:** 3

**Product:** ETC-1002

**Date:** Dec 18, 2018

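### SAP 19.4 gives creatinine in mmol/L, but its eGFR formula needs µmol/L; as written, every eGFR is about 2,900 times too high and the two eGFR abnormality rows cannot be reached

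*SAP*

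**What the plan says.** SAP 19.4 introduces its derivation with "The formula to calculate eGFR is" and sets

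eGFR = 186 × (creatinine / 88.4)^−1.154 × age^−0.203 × 0.742 (if female) × 1.210 (if black),

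"where creatinine is in mmol/L".

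The same section uses eGFR in two ways. Its list of laboratory abnormalities has one eGFR row below 15 and one from 15 to below 30 mL/min/1.73 m². It also plans that eGFR and "values of CK will be summarized by treatment group and by baseline eGFR categories (low, normal, high"). A separate row counts creatinine rises of more than 1 mg/dL.

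Protocol 11.7 (Renal Safety) adds two outputs that rest on eGFR: "Shift tables of eGFR category from baseline over the study, will be provided by treatment group", and "muscle-related AEs will be summarized by treatment group and by baseline eGFR category".

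For eligibility only, Protocol 6.2.2 takes eGFR from another source, "using central laboratory determined Modification of Diet in Renal Disease [MDRD] formula".

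**The concern.** The divisor and the stated unit do not fit together. Dividing by 88.4 turns creatinine in µmol/L into mg/dL. Applied to a value in mmol/L, it leaves a ratio 1,000 times too small, and the negative exponent turns that into an eGFR thousands of times too large.

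This is the only eGFR formula in either document. The central-laboratory MDRD value is named only for eligibility, and the safety laboratory list to which SAP 19.4 refers (Protocol Table 4) contains creatinine but not eGFR. A programmer following the SAP would therefore derive eGFR from this line.

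The risk is a false reassurance. Empty rows for eGFR below 15 and from 15 to below 30 in both arms look like a clean renal result. The DMC package in SAP Appendix 3 includes a table of abnormalities in laboratory parameters of interest, a title that matches the SAP 19.4 list, although its shell is not shown.

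**Working it through.** Neither document reports an eGFR result, so there is no plan figure to reproduce. The check evaluates the formula in both units.

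**Inputs.** From SAP 19.4: constant 186, divisor 88.4, creatinine exponent −1.154, age exponent −0.203, factors 0.742 and 1.210, and cut-offs 30 and 15. Assumed for illustration: age 65, not black, and the creatinine values below. These are not trial data.

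**What 88.4 is.** The documents do not explain it. With a creatinine molar mass of 113.12 g/mol (an outside physical constant), 1 mg/dL = 10 × 1000 / 113.12 = 88.40 µmol/L. The results below point the same way: only µmol/L gives usable values.

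**Inflation factor.** (Cr/1000)^−1.154 ÷ Cr^−1.154 = 1000^1.154 = 2,897. It does not depend on age, sex, race or creatinine.

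**Illustrative man.** 186 × 65^−0.203 = 186 × 0.4285 = 79.7, so eGFR = 79.7 × (Cr/88.4)^−1.154.

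| Creatinine (µmol/L) | eGFR, unit µmol/L | eGFR, same value entered in mmol/L | Row it belongs in |
|---|---|---|---|
| 88.4 | 79.7 | about 230,900 | none |
| 350 | 16.3 | about 47,200 | 15 to below 30 |
| 500 | 10.8 | about 31,300 | below 15 |
| 1,500 | 3.0 | about 8,800 | below 15 |

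**Can the rows be reached?** Inverting the formula, Cr = 88.4 × (k / cut-off)^(1/1.154), where k = 186 × age^−0.203 × the sex and race factors.

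- In µmol/L at age 65, eGFR 30 and 15 correspond to 206 and 376 µmol/L for a man, and to 159 and 290 µmol/L for a woman. Both rows are reachable.
- In mmol/L the same numbers apply in mmol/L. Over ages 18 to 100 and every sex and race combination, eGFR below 30 needs creatinine above 148 to 305 mmol/L, about 1,670 to 3,450 mg/dL. That equals a true eGFR below 30 / 2,897 = 0.0104. Neither row is reachable.

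**Does the creatinine row cover the loss?** Only in part. In the same man, a rise from 195 to 240 µmol/L is 45 / 88.4 = 0.51 mg/dL, below the 1 mg/dL row, while the correct eGFR falls from 32.0 to 25.2. Protocol 6.2.2 excludes patients below 30, so someone at 32 can be enrolled.

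**The case against.** The strongest reply is that this is a slip in a unit label with no likely effect on results. The constants, exponents and cut-offs agree with one another, and an eGFR near 230,000 in a healthy patient could hardly go unnoticed. The SAP's modification history records a dry run of this study's outputs before the final version. That makes a wrong output unlikely, but it does not correct the text. Under Protocol 11.1 the SAP governs the analysis and is appended to the study report, so eGFR results could not be reproduced from the stated method.

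A second reply is that µ may have become m when the PDF was read. Greek mu does survive in the hypotheses of SAP 18.1.2, so this is only a doubt, but the signed SAP should be checked first. If it reads µmol/L, the point falls.

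Third, SAP 19.4 says central-laboratory results will be reported, and SAP 19.4.1 defines low, normal and high by laboratory reference range. The baseline eGFR categories might therefore rest on a laboratory-reported eGFR. The SAP does not say so, and it gives a formula instead.

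Two further points limit the scope, and both stand. The eGFR-category shift tables and the muscle-event breakdown come from the protocol; SAP 19.4 plans shifts by normal range, and SAP 19.1.5 gives no eGFR breakdown. They are affected only if built on this formula. Also, low eGFR may be rare: Protocol 10.2.11.3.5 reports that no Phase 2 patient with a creatinine rise above 25% exceeded 1.8 mg/dL, which is an eGFR of about 40 in a man and 30 in a woman aged 65. Sparse rows would be plausible even with the right unit, which makes a wrongly empty row harder to spot. Creatinine also appears in the observed and change-from-baseline summaries, so the patient in the example above would not be invisible.

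**Conclusion.** The concern holds for the text as written. The stated unit inflates every derived eGFR by a factor of 2,897 and leaves both eGFR abnormality rows in the same section unreachable. This rests on 88.4 being the µmol/L to mg/dL conversion and on the SAP text reading mmol/L. Any effect on reported outputs depends on the formula having been programmed literally, which the documents do not show.

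The point is minor. It is confined to the two eGFR rows, the summaries of eGFR and CK by baseline eGFR category, and any protocol renal output built on the same derivation. The efficacy analyses, the creatinine-rise row, the renal terms in SAP Appendix 5 (such as "Blood creatinine increased"), eligibility by the central laboratory's eGFR and the protocol's eGFR withdrawal rule do not use this formula.

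**What to change.** After confirming the wording in the signed SAP, replace mmol/L with µmol/L in SAP 19.4. Alternatively, state there that the central laboratory's MDRD eGFR is used for all eGFR summaries and delete the formula. Then check which unit the analysis program used. The December 2018 SAP addendum says the planned analyses are complete, so the correction would take the form of a note to the SAP. The eGFR outputs, including any that went to the DMC, need re-running only if the program used mmol/L. The cost is one unit correction and one program check.

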#### 19.1.1. ALL TEAEs

Incidence of TEAEs will be presented by System Organ Class (SOC) and Preferred Term (PT) and also broken down further by maximum severity and relationship to study medication. Adverse events by the subgroups in [Section 18.2.4](#) with the exception of baseline LDL subgroup will also be presented.

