**19.1.5. MUSCLE RELATED ADVERSE EVENTS**

Muscle related events as reported on the general AE CRF will be summarized by maximum severity and SOC and PT. All muscle related events and details associated with it including cause and location will be provided in a listing.

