**19.4.1. LABORATORY REFERENCE RANGES AND MARKEDLY ABNORMAL CRITERIA**

Quantitative laboratory measurements will be compared with the relevant laboratory reference ranges in SI units and categorized as:

- Low: Below the lower limit of the laboratory reference range.
- Normal: Within the laboratory reference range (upper and lower limit included).
- High: Above the upper limit of the laboratory reference range.

In addition to the high and low quantitative laboratory assignments, Hy’s law criteria (≥3 × ULN for either ALT or AST, with accompanying total bilirubin >2 × ULN in the absence of other known causes) will be used to identify potential Hy’s law cases.

[REDACTED]

Version Number: 1.7  
 Version Date: 21Mar2018

[REDACTED]

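### The SAP's eGFR classes end in one undivided low class, so its shift table cannot show decline within it, and muscle events by baseline eGFR are missing from the SAP text

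*SAP*

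**What the plan says.** Protocol 11.7 (Renal Safety) lists three outputs, and the synopsis repeats them:

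- a summary of eGFR at baseline, and of CK, split by arm and by eGFR class at entry;
- for change over time: "Shift tables of eGFR category from baseline over the study, will be provided by treatment group"
- for muscle symptoms: "muscle-related AEs will be summarized by treatment group and by baseline eGFR category"

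Neither place gives cut-points for an eGFR category.

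SAP 19.4 carries over the first item and adds classes: "eGFR and values of CK will be summarized by treatment group and by baseline eGFR categories (low, normal, high". SAP 19.4.1 defines the lowest of these as "Low: Below the lower limit of the laboratory reference range", with nothing beneath it. Apart from a version for HbA1c and glucose by diabetes history, the only laboratory shift output is "Shift from baseline by visit according to normal ranges". Among the abnormality rows, SAP 19.4 has eGFR below 15, eGFR from 15 to below 30, and a creatinine rise of more than 1 mg/dL.

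On muscle events, SAP 19.1.5 says: "Muscle related events as reported on the general AE CRF will be summarized by maximum severity and SOC and PT". SAP 19.1.1 adds that adverse events by the Section 18.2.4 subgroups "with the exception of baseline LDL subgroup will also be presented". Those subgroups are CVD risk, diabetes history, age, race, gender, BMI and background therapy. None is renal.

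**The concern.** Two things looked wrong.

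First, a table the protocol specifies is absent from the SAP text. Protocol 11.1 gives the SAP precedence where the two differ on analysis, so an omission without explanation may mean that the table is never produced. Renal and muscular disorders are both categories of special interest in SAP Appendix 5, and every patient enters with statin intolerance.

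Second, the shift table cannot do what it is for in the patients of most interest. Exclusion criterion 2 removes only a screening eGFR below 30, so patients with impaired function from 30 upward can enter. For them, one open-ended low class hides any further decline.

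The renal question is not idle. Protocol 10.2.11.3.5 reports Phase 2 creatinine rises above 25% in 1 + 2 + 1 + 1 + 3 = 8 bempedoic acid subjects, none with creatinine above 1.8 mg/dL. Under that ceiling, a rise of more than 1 mg/dL needs a baseline below 1.8 − 1.0 = 0.8, so creatinine would have to more than double (1.8/0.8 = 2.25). The SAP's creatinine row is therefore set well above the kind of change already seen.

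**Working it through.** The plan states no figure on this point, so there is none to reproduce. The check has a textual part and an arithmetic part.

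**Text.** Of the three outputs in Protocol 11.7:

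- eGFR and CK by baseline eGFR category are in SAP 19.4.
- The eGFR-category shift is covered, if at all, by the normal-range rule. SAP 19.4 takes its list of laboratory outputs from Protocol 10.1.6.1, whose Table 4 lists creatinine but not eGFR, so even that table is not expressly assured.
- Muscle events by eGFR category are in none of SAP 19.1.1, 19.1.5 or 18.2.4.

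The low-to-low result follows from the definitions alone and needs no assumed number.

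**Arithmetic: what the other rows catch.** Inputs:

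- The SAP 19.4 eGFR formula, inverted: creatinine in mg/dL = (eGFR/k)^(−1/1.154), with k = 186 × age^(−0.203) × 0.742 if female × 1.210 if Black.
- The divisor 88.4 is read as converting µmol/L to mg/dL. The SAP says mmol/L; taken literally, that would inflate eGFR by 1000^1.154 ≈ 2,897.
- Sixteen profiles: ages 45, 55, 65 and 75, both sexes, with and without the race term.
- The lower reference limit for eGFR, which the documents do not give. I assume 60, with 90 as the alternative.

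Example, non-Black man aged 65: k = 186 × 65^(−0.203) ≈ 79.7. At eGFR 59, creatinine is (59/79.7)^(−0.867) = 1.30. At 31 it is 2.27. The rise is 0.97, just under the flag. For a non-Black woman of the same age it goes from 1.00 to 1.75, a rise of 0.75.

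| Assumed limit | eGFR start → end | Fall | Shift table | eGFR row below 30 | Creatinine rise, mg/dL | Profiles rising >1 |
|---|---|---|---|---|---|---|
| 60 | 59 → 31 | 47% | low to low | no | 0.73–1.22 | 5 of 16 |
| 60 | 50 → 26 | 48% | low to low | yes | 0.86–1.44 | 12 of 16 |
| 60 | 45 → 24 | 47% | low to low | yes | 0.89–1.50 | 12 of 16 |
| 90 | 89 → 46 | 48% | low to low | no | 0.53–0.88 | 0 of 16 |
| 90 | 75 → 40 | 47% | low to low | no | 0.57–0.96 | 0 of 16 |

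**Width of the gap.** A 47% fall stays at or above 30 only from a start of at least 30/(1 − 0.47) = 56.6. With a limit of 60 the window is therefore about 57 to 59; lower starts reach the 15 to below 30 row. With a limit of 90 the gap is much wider. Conversely, with a limit of 60 the last two rows of the table would appear as normal to low.

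**The case against.** The strongest reply is that nothing finer was taken away, and that renal decline is covered elsewhere.

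- **No grid was cut back.** A reader might infer that the SAP coarsened the protocol's eGFR categories. It did not: the protocol has no cut-points, and the SAP filled an undefined term. This stands. So does its corollary that a split at 60 is not a protocol requirement. If the laboratory's limit is 60, low against not-low already is that split, and CK by it is planned.
- **Decline does not go unseen.** A reader might infer that a near-halving of eGFR leaves no trace. That holds only for the shift table, and for the flags in the cases above. SAP 19.4 also summarises values, change and percent change by visit. Appendix 5 includes preferred terms for reduced filtration rate, raised creatinine and renal impairment. The DMC receives laboratory abnormalities and chemistry boxplots. This stands in part, since by-visit summaries describe groups and can dilute individual falls.
- **Very large falls are caught.** A fall from 89 to 31 would also be low-to-low under a limit of 90, but the creatinine row flags it: for a 65-year-old non-Black patient the rise is 0.91 to 2.27 = 1.36 mg/dL in a man, and 1.05 in a woman. It is not evidence of a gap.
- **The templates are unseen.** SAP section 8 leaves table format and content to templates that were not available. They could define the categories or contain the muscle table, so it cannot be said that the analysis is definitely lost. It can be said that the SAP text does not commit to it.
- **Weight.** Safety is descriptive, and SAP section 19 plans no between-arm tests by default. Protocol 10.2.11.3.5 also says that no Phase 2 subject withdrew for raised creatinine. This limits the consequence but does not excuse omitting a specified table.

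**Conclusion.** The point holds in a limited form. Two parts rest on the documents alone: the SAP text does not contain the muscle-event summary by baseline eGFR that Protocol 11.7 specifies, and a low, normal, high shift table cannot register worsening in a patient who starts low. That the 19.4.1 flags are what 19.4 means for eGFR is an inference, though the natural one.

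The size of the gap after the other rows are counted depends on a reference limit that the documents do not give. At 60 it is narrow: starts of about 57 to 59, with the creatinine flag missed in 11 of 16 profiles for a fall from 59 to 31. At 90 it is wide: falls of 47% to 48% from 75 or 89 meet no shift and no flag in any profile. The profiles are illustrative and are not weighted to the trial population.

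The documents do not support saying that the SAP overrode a finer protocol classification, or that renal decline would go undetected. Efficacy conclusions are unaffected.

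**What to change.** In SAP 19.4, replace low, normal, high for eGFR with fixed numeric categories that divide the range below normal, for example ≥90, 60 to <90, 45 to <60, 30 to <45, 15 to <30 and <15 mL/min/1.73 m². Using these, give shift tables by arm from baseline to each visit and to the worst post-baseline value. In SAP 19.1.5, restore the Protocol 11.7 summary of muscle-related TEAEs by arm and baseline eGFR category, collapsed (for example <60 and ≥60) if cells are sparse. The cut-points are a proposal; what matters is that classes exist below normal and are stated. Correct the creatinine unit in the eGFR formula at the same time.

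The data are already collected, so the cost is SAP wording and a few descriptive tables, some with small cells. The SAP addendum already adds tables after unblinding, including one on liver function, so the same route is open. Tables added that way should be labelled post hoc.
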